### APPENDIX III: STUDY ASSESSMENT INSTRUMENTS

**Note:** Study measures were chosen to overlap with those used in ALTE07C1, with the addition of the computerized CogState battery, which was chosen given its ability to be administered repeatedly over short intervals with negligible practice effects. The measure assigned initially by age will be used during the study even if the patient could move up to the next age level.

IQ*	Attention/ Working Memory	Verbal Memory	General	Parent Report
WISC-V** (Block Design Vocabulary)	CogState	CVLT-C**	Feasibility Interview	Feasibility Interview
	CMS** (Dot Location and Faces)			BASC-3*
	WISC-V** (Digit Span, Coding, Symbol Search, and Spatial Span subtests)			BRIEF
	Instructional WM**			ABAS-3
				BIS
				Socioeconomic Status Measure*
				Computer Use Questionnaire
				COG Language Preference Questionnaire

\* Baseline only

\*\* Optional psychologist-administered measure

#### Patient-Completed Measures

**Wechsler Intelligence Scale for Children – Fifth Edition** (WISC-V). The WISC-V measures intellectual functioning in children aged 6-16 (WISC-). For this project, the Vocabulary and Block Design subtests will be used at baseline only to estimate IQ. Additionally, working memory (Digit Span, Spatial Span), Coding and Symbol Search subtests will be administered at all time points for sites that have a psychologist to administer these measures.

**Children's Memory Scale** (CMS). The CMS is a test to assess verbal and visual memory in individuals 5-16 years of age. Dot Location and faces will be administered at all timepoints for sites that have a psychologist to administer these measures.

**California Verbal Learning Test – Children's Version** (CVLT-C). The CVLT-C involves verbally presenting a list learning task over the course of 5 trials. The test measures multiple aspects of how verbal learning occurs, or fails to occur, as well as the amount of verbal material learned. The CVLT-C is designed for individuals 5-16 years of age. The CVLT-C will be administered at baseline and 6-month follow-up for sites that have a psychologist to administer these measures.

**CogState** is a computerized testing software package that offers a range of semi-automated assessment modules for individuals aged 6-90 ([www.cogstate.com](http://www.cogstate.com)). The software can be installed on most computer systems and can be proctored by a research assistant with minimal training. Data are automatically uploaded, scored, and stored. Test batteries can be fully customized, and include tasks tapping visual motor, processing speed, visual attention, visual and verbal learning and memory, and working memory. A battery suitable for evaluating the core neurocognitive processes affected by cancer treatment would take between 12-18 minutes. Reliability is .77 with no practice effects when testing intervals are greater than one month. Age-based standard scores (mean = 100, SD 10) are computed for each task based on a normative sample of several hundred individuals. CogState tasks have been used successfully in trials of populations relevant to pediatric cancer patients. Specifically, it has been used with attention deficit hyperactivity disorder participants, for which CogState tasks discriminate between those with and without the diagnosis, and those on and off medication, as well as typically-developing children. In addition, CogState has been used in samples of patients with concussions, HIV/AIDS, pediatric cerebral malaria, and adult cancer patients. CogState is also currently being used in a multi-site trial funded by NCI to examine neurocognitive symptoms in long-term survivors of pediatric cancer. CogState will be administered at all time points.

**Instructional Working Memory Task** (Instructional WM). The Instructional WM is a brief task administered to children to evaluate functional application of WM skills. Children are asked to use task props (e.g., pencils, folders, etc.) to follow an increasingly complex set of instructions. For example, a child might be asked to “Pick up the blue ruler and put it in the red folder”. Scores are calculated based on a combination of accuracy in following the instructions weighted by how many actions the child is asked to perform with a single command. The instructional WM will be administered at all time points for sites that have a psychologist to administer these measures.

**Feasibility Interview:** In our previous trial with survivors of childhood cancer (R03-CA132570), we developed a 13-item survey for parents and children assessing technical feasibility, adherence, satisfaction, and ease-of-use. The Feasibility Interview will be completed by the parent by phone after session 12. Additionally both child and parent will complete a second feasibility interview during the post-intervention assessment.

### **Parent-Completed Measures**

**COG Language Preferences Questionnaire.** The child's language preference will be determined before testing begins using the parent-completed COG Language Preference Questionnaire. In order for the child to be enrolled, it must be determined that the neuropsychological testing procedures can be completed in English. If a parent is unable to complete the parent-report measures in English, the child will still be allowed to enroll but parent-report data will not be obtained. The COG Language Preference Questionnaire can be accessed on the COG website at:

<https://www.cogmembers.org/Prot/ALTE07C1/ALTE07C1COGlanguagerefquestionnaire.pdf>.

**Behavior Assessment System for Children, 3rd edition** (BASC-3). The BASC-3 describes the behaviors, thoughts, and emotions of children and adolescents. The parent rating scale will be utilized for individuals older than 2 years and less than 18 years of age. The questionnaire yields composite and scale scores in the domains of externalizing, internalizing, school, and other problems as well as adaptive skills and behavioral symptoms. The BASC-3 will be administered only at baseline.

**Behavior Rating Inventory of Executive Functioning** (BRIEF) is a parent-completed measure of behavioral executive functioning. For this study, items from the Metacognition subscales will be used. The BRIEF will be administered at all time points as an additional outcome measure.

**Adaptive Behavior Assessment System, 3rd edition** (ABAS-3). The ABAS-3 will be used for the assessment of adaptive skills in individuals older than 2 years and less than 18 years of age. Separate scale scores are available for 10 areas of adaptive skills. The ABAS-3 will be administered at baseline and 6 months following the completion of training.

**Brief Impairment Scale** (BIS). The BIS is a parent-completed, 23-item questionnaire evaluating social and functional impairment yielding scale scores for Interpersonal, School, and Self (personal) functioning. The BIS will be administered at baseline only.

**Feasibility Interview:** In our previous trial with survivors of childhood cancer (R03-CA132570), we developed a 13-item survey for parents and children assessing technical feasibility, adherence, satisfaction, and ease-of-use. The Feasibility Interview will be completed by the parent by phone. Additionally the child will complete a feasibility interview during the post-intervention assessment.

**Socioeconomic Status Measure:** The Socioeconomic Status measure is a brief measure consisting of questions related to parents' marital status, education, and work. This measure will be completed by parents at baseline only.

**Computer Use Questionnaire:** The Computer Use questionnaire assesses the frequency and nature of the child's computer use at home and at school. It will be completed by parents at baseline and at 6-month follow-up.

**APPENDIX IV: SOCIOECONOMIC STATUS MEASURE****Obtain at Baseline.****Subject:** \_\_\_\_\_**Subject ID:** \_\_\_\_\_**Date:** \_\_\_\_\_

We would like to ask you a few questions about yourself and your family. The questions ask about educational background and current work. Please answer all of the questions as completely as possible.

## 1. Are you (please check all that apply):

- Single: (Please specify further)
  - Never married
  - Separated
  - Divorced
  - Widowed
- Married: (Please specify further)
  - To the other parent of my child with brain tumor
  - To someone else
- Living with a significant other/partner: (Please specify further)
  - With the other parent of my child with brain tumor
  - With someone else
- Not living with, but have a partner: (Please specify further)
  - The other parent of my child with brain tumor
  - Someone else
- In a civil union

## 2. If you are not living with the other parent of your child, how often does that parent see your child?

- Not applicable, I live with the other parent
- Less than once per month
- A few times per month
- About once per week
- A few times per week
- Almost every day

## 3. What was the highest grade or level of school that the main caregiver has completed?

- Grade school (grades 1-8)
- High school, but didn't graduate
- High school, completed
- Training after high school, other than college
- Some college
- College graduate
- Post graduate level
- Unknown

5a. What kind of work are you doing? (What is your occupation?)

(For example: homemaker, retail sales, machinist, etc.)

5b. What are your most important activities or duties?

(For example: selling merchandise, filing, supervising, etc.)

5c. What kind of business or industry is this?

(For example: retail shoe store, automobile manufacturing, state labor department, etc.)

**PLEASE SKIP #6 and 7a, b, c if you are living alone.**

6. What was the highest grade or level of school your spouse/significant other has completed?

- Grade school (grades 1-8)
- High school, but didn't graduate
- High school, completed
- Training after high school, other than college
- Some college
- College graduate
- Post graduate level
- Unknown

7a. What kind of work is your spouse (significant other) doing? (What is his/her occupation?)

(For example: homemaker, retail sales, machinist, etc.)

7b. What are his/her most important activities or duties?

(For example: selling merchandise, filing, supervising, etc.)

7c. What kind of business or industry is this?

(For example: retail shoe store, automobile manufacturing, etc.)

## APPENDIX VA: PARENT FEASIBILITY AND ACCEPTABILITY INTERVIEW

### Obtain Following CT Session 12 and After Training Completion

Subject: \_\_\_\_\_

Subject ID: \_\_\_\_\_

Date: \_\_\_\_\_

Session: 12 25

Respondent: \_\_\_\_\_

#### *Technical feasibility:*

1. Did the computer program work every time you tried it? Yes No

a. If no, please describe problems: \_\_\_\_\_  
\_\_\_\_\_  
\_\_\_\_\_

2. Did you have any problems with the computer itself? Yes No

a. If yes, please describe problems: \_\_\_\_\_  
\_\_\_\_\_  
\_\_\_\_\_

#### *Adherence:*

1. How often did your child resist/protest/complain about completing exercises on the computer this month?

Never      Rarely      Sometimes      Often      Always

2. How did you typically respond to your child when s/he resisted doing exercises?

\_\_\_\_\_  
\_\_\_\_\_  
\_\_\_\_\_

3. Do you think your child would have completed the exercises even without the opportunity to earn a gift card? Why or why not?

---

---

---

a. Which of the following might make your child more likely to complete all the exercises?

More money on the gift cards.  
 More frequent rewards.  
 Fewer required sessions.  
 Shorter sessions.

***Satisfaction / Ease of use:***

1. Using the following scale, how easy or difficult was it for your child to use the computer to do the exercises in the following areas?

very easy    somewhat easy    neither easy/hard    somewhat hard    very hard

a. turning on/logging in: \_\_\_\_\_

b. starting the program: \_\_\_\_\_

c. using the mouse: \_\_\_\_\_

2. Using the following scale, how easy or difficult was it for your child to do the exercises?

very easy    somewhat easy    neither easy/hard    somewhat hard    very hard

3. Using the following scale, how often were you present with your child while s/he was doing the exercises?

Never    Rarely    Sometimes    Often    Always

4. Using the following scale, how often did your child experience physical pain or discomfort while using the computer program?

Never    Rarely    Sometimes    Often    Always

If any response other than "never": Please describe the physical pain or discomfort your child experienced: \_\_\_\_\_

---

---

5. Using the following scale, how often did your child experience frustration while using the computer program?

Never    Rarely    Sometimes    Often    Always

6. Using the following scale, how often did your child feel bored during the computer exercises?

Never            Rarely            Sometimes            Often            Always

7. Using the following scale, how often did your child enjoy completing the exercises?

Never            Rarely            Sometimes            Often            Always

8. Using the following scale, how satisfied were you with your child's participation in the study this month?

Very dissatisfied    Somewhat dissatisfied    Neither    Somewhat satisfied    Very Satisfied

Other comments or concerns: \_\_\_\_\_

---

---

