Participants meeting criteria for randomization will be trained in the use of the *Cogmed* programs in the clinic by study personnel (see below and [Appendix II](#)). In order to avoid biasing the sample towards socioeconomically advantaged individuals, participants without dedicated access to an adequate home computer will be provided with a laptop computer or tablet device for the duration of the intervention, regardless of whether they are assigned to the adaptive or non-adaptive arms. Moreover, families without available internet access will be provided with wireless internet cards for the duration of the intervention. The intervention will consist of three to five, 15- to 45-minute sessions (younger children practice for less time) per week for 5 to 9 weeks (total = 25 sessions). If patients do not complete the training within 9 weeks, they will be removed off protocol therapy but will remain on study and will receive the post-intervention and follow-up assessment. Similarly, patients who do not complete the 25 sessions for any reason will receive the post-intervention and follow-up assessment unless they meet Off Study Criteria (see [Section 5.0](#) below). Thus, using an intent-to-treat approach, every effort will be made to obtain post-intervention and follow-up data on every child who is randomized, unless they meet Off Study Criteria.

To assist participants as they complete the intervention, a treatment “coach” will be available to parents and children by phone throughout the intervention period. Weekly phone contact with the coaches will be scheduled so that compliance and feasibility data may be collected and so that any problems (e.g., training issues, adverse events, technical problems) can be addressed efficiently. Of note, *Cogmed* routinely provides technical assistance to individuals using the programs at no additional cost. Additionally, to promote compliance and maintain children’s interest in the program, participants will earn \$10 gift cards (or comparably valued prizes/compensation) after completion of approximately each third of the training (total = \$30). This incentive schedule is similar to the one used in the trial of this program in survivors of childhood cancer, and was associated with a compliance rate of 85%.

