### 6.3.3 Analysis Plan

Compliance rate (the portion of patients who complete at least 80% of the sessions within 9 weeks) will be calculated for the overall study population and each arm separately. Z-test for binomial proportion with continuity correction will be used to examine if the overall compliance rate is lower than the target of 75%. Confidence intervals of the estimated compliance rate will be constructed for the overall study population and for each arm separately. We will use Fisher's exact test to examine if there is any significant difference in the compliance rate between the 2 arms. Compliance data on the number of sessions completed for all patients and for patients on each arm will also be described by summary statistics such as mean or median, and compared between the 2 arms by two-sample t-test or Wilcoxon rank sum test. We will use descriptive and summary statistics to report parent and child ratings of the intervention's technical feasibility, ease-of-use, and satisfaction across the three time-points that this information is collected. In addition, we will use descriptive and summary statistics to detail the total number of patients enrolled, determine rates and reasons for non-eligibility and patient refusal for randomization, characterize socioeconomic status of the parents and computer usage for the patients and evaluate the number and type of adverse incidents reported through the questionnaires (if any). We will use a series of t-tests (for continuous variables) and Chi-square tests or Fisher's exact tests (for non-continuous variables) to examine potential differences between eligible patients who accept or decline to be randomized to the treatment phase, between participants who are compliant (i.e., 80% of sessions completed) and noncompliant, and for other medical, psychosocial, and contextual factors.

The analysis of preliminary efficacy will be conducted on an intent-to-treat basis. We will use descriptive/summary statistics to summarize the objective and the subjective measures of attention and WM in each arm and the differences between the 2 arms on the post-intervention/6-month assessment or on the difference between the post-intervention/6-month assessment and the baseline assessment. Linear regression models using the post-intervention/6-month assessment as outcome will also be used to estimate the effect size of intervention with adjustment for potential confounders including the baseline assessment. Linear

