## APPENDIX VB: CHILD FEASIBILITY AND ACCEPTABILITY INTERVIEW

### Obtain After Training Completion

Subject: \_\_\_\_\_

Subject ID: \_\_\_\_\_

Date: \_\_\_\_\_

1. Using the following scale, how often did you feel frustrated while using the computer program?

- Never
- Rarely
- Sometimes
- Often
- Always

2. Using the following scale, how often did you feel bored during the computer exercises?

- Never
- Rarely
- Sometimes
- Often
- Always

3. Using the following scale, how often did you enjoy the computer exercises?

- Never
- Rarely
- Sometimes
- Often
- Always

Comments:

---

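### Physical discomfort during training is asked only of the parent, so the questionnaire-based adverse-incident count can miss what the child felt (minor)

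*Combined protocol and SAP*

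**What the plan says.** The parent interview (Appendix VA, satisfaction and ease of use) asks in item 3 "how often were you present with your child while s/he was doing the exercises" and in item 4 "how often did your child experience physical pain or discomfort while using the computer program". Both are rated from Never to Always. Any answer to item 4 other than Never leads to a request to describe the problem. Items 5 to 7 then cover frustration ("how often did your child experience frustration while using the computer program"), boredom and enjoyment.

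The child interview (Appendix VB) has three rated items: "how often did you feel frustrated while using the computer program", "how often did you feel bored during the computer exercises" and "how often did you enjoy the computer exercises". It closes with a line for comments.

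Section 4.6 and Table 1 schedule the parent interview by phone after session 12 and again at the post-intervention assessment. The child is interviewed once, post-intervention.

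Section 6.3.3 plans, by descriptive statistics, to "evaluate the number and type of adverse incidents reported through the questionnaires (if any"). Section 4.3 separately schedules weekly coach calls, partly so that "any problems (e.g., training issues, adverse events, technical problems) can be addressed efficiently".

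**The concern.** Pain and discomfort are felt by the child. The parent knows of them only by seeing them or being told. The child sits for an interview after training and is asked to rate frustration and boredom on the same five-point scale, yet is not asked about discomfort. If the adverse-incident summary rests on the questionnaires, its physical component rests on the parent's knowledge, plus whatever a child volunteers under comments.

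What is at stake is how complete a descriptive summary is. Section 2.0 says the results will serve as pilot data for a larger trial, and Section 4.1 expects almost all participants to be on chemotherapy during this period. An accurate account of discomfort at the computer would help in planning that trial. Discomfort that nobody asked the child about is hard to recover later.

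**Working it through.** The plan states no figure on this point, so there is none to reproduce. The check compares the two forms and follows the item into the analysis.

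**1. Item by item**

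| Topic | Parent form (Appendix VA) | Child form (Appendix VB) |
|---|---|---|
| Parent present at sessions | item 3 | not applicable |
| Physical pain or discomfort | item 4, with description | none |
| Frustration | item 5 | item 1 |
| Boredom | item 6 | item 2 |
| Enjoyment | item 7 | item 3 |
| Open remarks | closing line | closing line |

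The parent form has 2 technical + 3 adherence + 8 satisfaction items = 13 numbered items, which matches the 13-item survey described in Section 4.6. The child form has 3. Its items follow parent items 5 to 7 in order; item 4, directly before them, has no counterpart. The child form runs through to its closing comments line, so the omission does not look like missing text.

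**2. Other instruments.** Appendix III describes the remaining parent questionnaires as covering behaviour, executive function, adaptive skills, impairment, socioeconomic status, language and computer use. None is described as asking about discomfort during training. I take the questionnaires in Section 6.3.3 to include the two feasibility interviews; the section does not list them.

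**3. Who is asked, and when.** The parent is asked item 4 after session 12 and after training. Section 4.5.3 could be read as adding a parent interview at 6 months, which Table 1 does not show. On either reading the informant for this item is the parent.

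**4. Other routes.** Section 4.4 requires phone meetings at least weekly, and Appendix II gives coaches a script that re-evaluates medical factors among others. These calls can bring discomfort to light. Section 6.3.3 does not say that what they record enters the incident summary.

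**5. Result.** Discomfort reaches the count if the parent reports it, or if the child or parent volunteers it as an open remark. Discomfort known only to the child and not volunteered does not. Discomfort reported only to a coach enters only if someone decides, outside the written plan, to add it.

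**The case against.** The case against giving this much weight is good, and most of it stands.

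- **Safeguards exist.** The parent is asked twice, both forms invite open remarks, Section 3.2.4.1 requires a caregiver able to oversee training, and coaches call weekly. A parent need not witness discomfort to report it, because the child can tell them. These points reduce the gap. They do not close it, since none puts the question directly to the child, and the coach calls are not a named source for the count.
- **The trial does not test safety.** A reader might infer that it sets out to confirm the program's lack of known adverse effects, so that a low count would become false evidence of safety. The documents do not support this. Sections 1.1 and 1.2 set feasibility and effect-size objectives, Section 6.3.1 lists no safety endpoint, and no decision depends on the count.
- **Parental absence is not shown.** A reader might infer from item 3 that the sponsor expects parents to be away. Item 3 uses the same frequency scale as several other items, so it shows only that presence is allowed to vary.
- **A twofold error cannot be claimed.** With no reports among 60 children, the exact one-sided 95% upper limit is 1 − 0.05^(1/60) = 4.9%. If parents noticed only half of cases it would be 0.0487/0.50 = 9.7%. That ratio is just 1/0.50, the assumption restated. The documents give no parental detection rate, and the plan calculates no such limit.
- **The instrument was carried over** from the earlier survivor trial (Section 4.6). That explains the short child form but gives no reason for leaving out this item.

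**Conclusion.** The point holds as a minor gap in measurement. The one physical-harm question goes to the parent alone, the child form omits it while repeating its neighbours, and the planned summary names the questionnaires and not the coach calls. The descriptive count can therefore miss discomfort that the child felt and the parent did not know of.

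No size should be attached. As an illustration on assumptions that are not in the documents, take 60 children, true discomfort in 10% to 30%, and parents aware of 90% to 50% of cases. The number missed then runs from 60 × 0.10 × 0.10 = 0.6 to 60 × 0.30 × 0.50 = 9. A range that wide reflects the assumptions and is no estimate for this trial.

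The compliance endpoint in Section 6.3.1, its test and its power do not use this item and are unaffected. The conclusion rests on the child form being complete as shown and on the reading of the questionnaires given above.

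**What to change.** 1. Add the discomfort item, reworded for self-report, to Appendix VB as a fourth item, with the same follow-up asking for a description.
2. State in Section 6.3.3 that an incident is counted if the parent or the child reports it. Any answer other than Never is a natural threshold, since it already prompts the parent's description.
3. State that adverse events recorded in coach calls are included. Show the source of each report (parent, child, coach call), and count a child reported by more than one source once in the per-child total.
4. If some children have already been interviewed, give the number who were asked the new item.

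A breakdown by the five levels of parental presence is not worth adding: with about 60 families and probably few reports, most cells would be close to empty.

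The cost is one question on a three-item form at a visit already planned, and a source column in the incident table. The one downside is that asking children directly, and adding the calls, may raise the reported count; showing the source lets a reader see why.
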